1 General Information

1.3 Identification of principal investigators in our center

[name]: IDIBAPS, Cellex 3A, [name]
[name]: Fundació Clínic. IDIBAPS. [name]

2 Justification

The discovery of the encephalitis associated with antibodies against neuronal surface antigens initiated a new era in the study of autoimmune diseases of the central nervous system (CNS) with important implications for neurology, psychiatry and neurosciences in general (1). In contrast to CNS disorders related to antibodies against intracellular proteins, patients with autoimmune encephalitis and antibodies against neuronal surface proteins, such as the NMDA receptor (NMDAR) or LGI1 protein, may or may not have an underlying tumor, the antibodies are directed against extracellular epitopes of the antigens, and have mild to moderate brain cytotoxic T cell infiltrates with predominant pathogenic mechanisms related to B cells (2). In these cases, the antibodies reversibly alter the structure and function of the target antigens (NMDAR or LGI1) and affect synaptic plasticity without causing major neuronal loss (3-5). Therefore, the neurologic alterations are potentially reversible by eliminating the antibodies or the cells that produce the antibodies (B cells, plasma cells) (6). Studies in the United Kingdom (7), The Netherlands (8), United States (9) or Spain (10) suggest that the encephalitis mediated by this category of antibodies directed against synaptic proteins or receptors are as frequent as herpes simplex encephalitis, and that anti-LGI1 encephalitis is the second most common antibody-mediated encephalitis after anti-NMDAR encephalitis (8). Because the treatment and follow-up of these patients usually require a wide spectrum of specialists in neurology, psychiatry, pediatrics, intensive medicine and rehabilitation, the impact of these diseases has been wide.

The current project will focus on anti-LGI1 encephalitis, which was discovered by our group in 2010. It mildly predominates in men (M:F, 6:4) and mostly older than 60 years (11, 12). The incidence is unclear; it has been estimated to be ~1 per million persons per year, but it is likely underestimated (8). All patients with anti-LGI1 encephalitis have IgG LGI1 antibodies (predominantly IgG4) in CSF and about 95% in serum (13). The disease has two distinct clinical phases: The acute phase in which the majority of patients develop severe short-term memory deficits (unable to remember events or experiences that occurred a few minutes earlier). This memory impairment can be preceded or accompanied by one or more of the following: hyponatremia (60% of patients), a highly distinctive type of seizures called facio-brachial dystonic seizures (~40% of patients), along with confusion, irritability and other types of focal seizures or less frequently, generalized seizures (11-15). In addition, many patients at this stage have symptoms of REM sleep behavior disorder (16). In this stage, the CSF may show pleocytosis or mild increase of proteins, the EEG is usually abnormal, and in ~60% of the patients the MRI shows typical increased FLAIR signal in medial temporal lobes (11). There is a clinical sub-phenotype (~13% of patients) in which the disease presents as a rapidly progressive cognitive decline without the indicated FLAIR MRI changes (15). About 70% of patients improve rapidly with corticosteroids and immunotherapy (eg, intravenous immunoglobulins and/or plasma exchange), but the improvement is often partial. After the acute phase, there is a chronic or residual phase which represents the interval from improvement of initial symptoms until the disease is considered no longer active and the remaining symptoms are thought to be irreversible. This chronic phase may take several months (it has been less well studied), and is characterized by the absence of CSF pleocytosis and inflammatory MRI changes (albeit this may show residual hippocampal atrophy), and very low or undetectable titers of serum antibodies. Most patients are unable to return to their job or previous activities due to residual (irreversible) memory or cognitive deficits accompanied by signs of moderate brain atrophy (14, 15). In addition, we and others have shown that about 27-35% of patients have relapsing symptoms after improving from the acute phase (14, 15). Although acute symptomatic seizures (facio-brachial dystonic and others) occur in ~90% of patients during the acute phase of the disease, less than 10% of patients develop chronic epilepsy often associated with hippocampal sclerosis (17). Therefore, the prevailing concept on this disease suggests a syndrome and clinical course in which the acute phase shows rapid, albeit partial, response to immunotherapy, and the symptoms of the chronic phase represent a burnout or irreversible process, in which the disease is no longer active, and the potential improvement of remaining symptoms is uncertain. As discussed later, we challenge this concept in the current proposal.

LGI1 is a neuronal secreted protein that forms a synaptic bridge, interacting at the presynaptic level with ADAM23 and the Kv voltage-gated potassium channels, and at the post-synaptic level with ADAM22 and the AMPA receptors (11). The protein has a leucine-rich domain and 7 repeats of about 50 amino acids (EPTP domains). We and others have shown that antibodies from patients with anti-LGI1 encephalitis react with epitopes contained in the leucine-rich domain and the EPTP domains (5, 18). Moreover, the indicated responsiveness to immunotherapy (compared with patients with classical paraneoplastic limbic encephalitis), and the demonstration that in cultured neurons patients' LGI1 antibodies disrupted the interaction of LGI1 with its synaptic partners (ADAM proteins) without causing neuronal death, suggested the pathogenicity of the antibodies (19). However, without an animal model it remained unclear whether the antibodies were able to cause clinical symptoms. We achieved this objective by adapting a mouse model (we previously developed for NMDAR antibodies) of passive transfer of patients' LGI1 antibodies (4). In this model, mice underwent a continuous (14 days) cerebroventricular infusion of patients' CSF enriched with LGI1 antibodies via

subcutaneously implanted osmotic minipumps connected with catheters to the lateral ventricles. Mice infused with patient's LGI1 IgG, but not control IgG, developed memory deficits which progressively recovered after the antibody infusion stopped. Furthermore, comprehensive confocal, patch-clamp and field potentials analyses in the CA1 region of the hippocampus showed that patients' IgG disrupt several LGI1-associated pathways, altering presynaptic and postsynaptic signaling, and causing neuronal hyperexcitability, decreased plasticity, and reversible memory deficits.

Clinical and immunological challenges pending to be solved

Although the advances described above are notable and were achieved in just a few years, there are still important gaps of knowledge related to the chronic phase of the disease and underlying immune-mechanisms that we are aiming to address in this proposal.

1- The concept that patients with autoimmune encephalitis respond rapidly to immunotherapy, and that most of the remaining symptoms a few months after disease onset are caused by irreversible brain alterations is inaccurate, as we recently reported for anti-NMDAR encephalitis (20). We postulate that the same occurs for anti-LGI1 encephalitis. In a recent prospective study in which 24 patients with anti-LGI1 encephalitis were invited to come to our center for additional clinical investigations during the chronic phase of the disease, we found that most (90%) had deficits in 1 or more of 6 cognitive domains at the first visit (V1), 65% had cognitive deficits at V2 (6 months), and 62% at V3 (1 year). In addition, at V1, about 90% of the patients had other symptoms (facio-brachial dystonic or focal seizures; REM sleep behavior disorder, insomnia) that were missed by patients, family members, or physicians. Some of these alterations were still present in 55% of patients at V2, and in 40% at V3. The main reason for the symptoms being unnoticed was that they often occurred at night or were identified with EEG or video-polysomnography.

Indeed, these studies showed that patients considered asymptomatic (regarding facio-brachial dystonic seizures, other seizures, or sleep disorder) had evidence of these types of symptoms with the appropriate tests. Because these clinical alterations were under-recognized, patients were no longer receiving immunotherapy or were undertreated with anti-seizure medications. These findings, which need to be confirmed and expanded with additional studies, are novel and important because they challenge the current prevailing view that facio-brachial dystonic seizures and other types of seizures, develop early in the course of the disease (often as first symptom) and resolve rapidly with immunotherapy (21). We also found that actimetry (or actigraphy assessed with a wrist-watch like device) may help to track these nocturnal seizures at home, an observation that we propose to assess in the current proposal.

2- A question that remains to be answered for any type of autoimmune encephalitis is whether prompt cognitive rehabilitation can improve, reverse, or shorten the process of recovery. There is evidence that this type of rehabilitation improves the cognitive functions of patients with other disorders even in presence of irreversible neuronal damage (22), and there is preliminary data suggesting that it is also effective in patients with multiple sclerosis. Therefore, it is likely that cognitive rehabilitation will be effective in disorders such as the autoimmune encephalitides in which the alterations are mainly caused by neuronal dysfunction rather than by irreversible cell damage. For anti-LGI1 encephalitis (which typically occurs in patients older than 60 years and associates with protracted cognitive deficits) any improvement in cognitive functions would represent a major change in their quality of life, facilitating their return to previous baseline personal and professional activities.

3 - Modeling the disease in mice using active immunization with LGI1 peptides. For autoimmune encephalitis associated to antibodies against neuronal cell-surface proteins or receptors, the demonstration that patients' antibodies are pathogenic suggests that most of the symptoms are potentially reversible by removing the antibodies or antibody producing cells (memory B cells and plasma cells). In addition, knowing how the antibodies alter the protein targets (eg, antibody-mediated internalization of NMDAR for anti-NMDAR encephalitis,(6) or the indicated pre- and postsynaptic changes in LGI1-interacting proteins such as VGKC or AMPA receptors) may lead to novel treatment strategies such as allosteric modulation of receptor targets. We have demonstrated all these features in several animal models of passive cerebroventricular transfer of patients' antibodies, including NMDAR and LGI1 antibodies (8). However, despite the utility of these models, they do not fully reproduce the immunobiology of the disease and do not associate with inflammatory infiltrates. Moreover, passive infusion of antibodies to ventricles leads to a predominant diffusion of the antibodies to the hippocampus but not the entire brain, and have effects for only 12-15 days (until they are cleared from brain). To overcome these limitations we recently developed an active immunization model of anti-NMDAR encephalitis that we propose to adapt for anti-LGI1 encephalitis. Animals are immunized with selected peptides with highly immunogenic sequences along with the adjuvant Addavax (which primes B cell-mediated immune responses). Animals develop their own pathogenic antibodies, and brain inflammatory infiltrates allowing the assessment of how the autoimmune response leads to symptoms. It also, provides a chronic phase of the disease (71 days) during which different treatments can potentially be tested.

15. Arino H, et al. Anti-LGI1-associated cognitive impairment: Presentation and long-term outcome. *Neurology* 2016;87:759-765.
16. Iranzo A, et al. Rapid eye movement sleep behavior disorder and potassium channel antibody-associated limbic encephalitis. *Ann Neurol* 2006;59:178-181.
17. de Brujin M, et al. Evaluation of seizure treatment in anti-LGI1, anti-NMDAR, and anti-GABABR encephalitis. *Neurology* 2019;92:e2185-e2196.
18. Ramberger M, et al. Distinctive binding properties of human monoclonal LGI1 autoantibodies determine pathogenic mechanisms. *Brain* 2020;143:1731-1745.
19. Ohkawa T, et al. Autoantibodies to epilepsy-related LGI1 in limbic encephalitis neutralize LGI1-ADAM22 interaction and reduce synaptic AMPA receptors. *J Neurosci* 2013;33:18161-18174.
20. Guasp M, et al. Clinical characterisation of patients in the post-acute stage of anti-NMDA receptor encephalitis: a prospective cohort study and comparison with patients with schizophrenia spectrum disorders. *Lancet Neurol* 2022;21:899-910.
21. Irani SR, et al. Faciobrachial dystonic seizures: the influence of immunotherapy on seizure control and prevention of cognitive impairment in a broadening phenotype. *Brain* 2013;136:3151-3162.
22. Diaz Baquero AA, et al. The Effectiveness of GRADIOR: A Neuropsychological Rehabilitation Program for People with Mild Cognitive Impairment and Mild Dementia. Results of a Randomized Controlled Trial After 4 and 12 Months of Treatment. *J Alzheimers Dis* 2022;86:711-727.

3 Hypotheses of the study

The hypotheses of this proposal are:

- 1) Close follow-up and comprehensive studies (neurological, cognitive, epileptic activity, sleep dysfunction) will improve our understanding of the clinical phenotype of anti-LGI1 encephalitis, particularly the chronic phase. Determination of biomarkers of autoimmunity, inflammation, and neuronal degeneration in patients' serum will serve to follow-up disease activity.
- 2) Patients with anti-LGI1 encephalitis who receive prolonged cognitive training (eg, 6 months) will show better performance in memory and executive tests than patients who did not receive cognitive training (previously studied external control group).
- 3) A mouse model of active immunization with LGI1 peptides will reproduce better the disease than a previous model of passive transfer of antibodies that leads to antibody diffusion highly limited to hippocampal regions, absent inflammatory infiltrates, and changes that last for only 12-15 days. In contrast, an active immunization model will lead to inflammatory infiltrates and LGI1-specific B-cell responses involving the entire brain in association with: synthesis of LGI1 antibodies, synaptic alterations mediated by changes on LGI1 and interacting proteins, and behavioral alterations. We postulate that the alterations in all these paradigms will be long-lasting, reproducing not only the acute phase but also the chronic phase of the disease.

4 Objectives and aims of the study

The indicated hypotheses will be tested in **3 objectives**:

- 1)** Determine the main clinical features (neurological, cognitive, EEG, video-polysomnography) of patients with anti-LGI1 encephalitis during the chronic phase of the disease, and assess serum biomarkers of autoimmunity/inflammation (LGI1 antibodies, RNA/NanoString analysis of targeted gene expression related to activation/function of B cells, T cells, microglia, and other interleukin/chemokine signaling) and neuronal degeneration (NfL levels).
- 2)** Assess whether remote cognitive training during the first 6 months following initial hospital discharge modifies clinical outcome. Findings will be compared with a previously studied external control group of patients with anti-LGI1 encephalitis but who did not receive remote cognitive training.
- 3)** Develop an animal model of active immunization using a repertoire of LGI1 peptides derived from the main immunogenic regions of LGI1. Determine the presence of LGI1 antibodies in serum/CSF and brain inflammatory infiltrates using immunohistochemistry. Examine how these immunological alterations alter the pre- and postsynaptic LGI1-interacting proteins (VGKC, AMPA receptor) and cause neurological symptoms; for this we will use confocal synaptic imaging, electrophysiology, and a standard panel of behavioral tests. In addition, we will assess the same serum biomarkers of autoimmunity/inflammation (RNA/NanoString analysis) as those used in patients, but with primers adapted to mouse.

4.1 Primary and secondary variables

1. Clinically characterize the post-acute stage of anti-LGI1 encephalitis, provide tools to remotely follow cognitive, behavioral and psychiatric deficits, and assess the impact of a cognitive rehabilitation program.
 - 1.1. Cognitive assessment: Battery of 16 tests encompassing 8 cognitive domains: 1) intelligence quotient; 2) working memory; 3) learning and memory; 4) psychomotor speed; 5) executive functions; 6) selective and sustained attention; 7) language; 8) visuospatial perception. Total time ~2.5h.
 - 1.2. Polysomnogram (PSG) will be adapted to patient's sleep habits (~23:00 to 07:30) using a digital polygraph (Deltamed). This includes EEG in 43 scalp channels + 11 channels for electrooculography, electrocardiography, electromyography, and audiovisual recording (sampling rate 256 Hz). Sleep stages will be scored manually (AASM criteria) using 30-s epochs, with modifications depending on sleep alterations. Data will be analyzed off-line in Python.
 - 1.3. EEG (43 channels, 512 Hz) will be obtained the morning after the sleep study.
- 1.4. Brain MRI studies will be conducted on a 3 Tesla Prisma scanner using a 32-channel head coil. Scanning takes include 3D T1-weighted in sagittal plane; T2*axial EPI; axial diffusion weighted EPI; 3D sagittal FLAIR. MRI will not use contrast in the procedure.
- 1.5. Actimetry: at each presential visit, all patients will be provided with an actimeter (Actiwatch AW7, CamTech Ltd., UK), which is an accelerometer wrist-watch like device that measures movement, with the goal to determine whether at home it shows abnormalities that

correlate with some of the seizures and sleep alterations (eg, awakenings, sleep fragmentation) noted during the in person visit and video-polysomnography. In practical terms for patients, it will be akin to wearing a wristwatch (patients will leave the hospital with the device placed in the non-dominant wrist and in use, so that they will not need further instructions) for 1 week at home (day and night) after each presential visit (V1, V2 and V3). At the end of the week, a courier will collect it, and over the course of the following month, the recordings will be downloaded and analyzed with the MotionWare software (CamTech Ltd., UK). Actimetry is a test used in routine clinical care in the sleep disorders clinic and can be requested from the SAP request form. As with other tests, actimetry studies are identified with the patient's history number. Once the files are downloaded, in the case of research studies, they are identified with the patient's study code and stored in the F:/ folder. Only principal investigators can access the patient-code relationship.

1.6. Serum and CSF biomarkers of autoimmunity/inflammation and neuronal degeneration. Left over samples of blood and CSF that were obtained and stored during the acute stage of the disease (by the time of symptom onset and local hospital admission) will be obtained from the core laboratory (CBD) for patients seen at our center or will be sent to our center from the referring doctors. The diagnosis of anti-LGI1 encephalitis requires demonstration of antibodies in CSF (serum can be negative); thus, initial CSF studies form part of standard of care in this disease. For the current study, the left-over routine care serum and CSF samples from the recruited patients will be used after their informed consent. For patients followed at our institution, we will take advantage of a regular follow-up visit to inform about the study and obtain their consent. For patients cared for at other hospitals, the referring doctors will explain the possibility of participating in the current study and, if the patients consent, we will contact them to provide further explanations and in such case obtain the informed consent. Serum and CSF collection procedures will be as performed in the routine clinical practice of these patients. These acute samples will be tested for the indicated (see below) biomarkers of autoimmunity, inflammation, and neuronal injury. We are a referral center for the diagnosis and study of this disease, and therefore we have ample experience in receiving and handling the samples.

During the post-acute stage (by the time that patients will come to Hospital Clínic de Barcelona), blood and CSF samples will be obtained for identical studies as those performed in the acute stage serum and CSF samples. Two lumbar punctures will be performed, after informed consent, one at the first presential visit (V1) and the other at the last presential visit (V3).. Based on a recently published pilot study and extensive experience with the disease, all patients at V1 have cognitive, sleep and epileptic alterations and most still have residual deficits at V3; thus, the CSF studies are important for investigations on biomarkers of disease severity, outcome and prognosis, and for better optimization of therapeutic options. They include:

- LGI1 Antibodies, determined with brain tissue immunohistochemistry and cell-based assays.
- HLA genotyping, performed by standard techniques based on DNA-PCR and polymorphism identification by reverse hybridization with specific probes and fluorescence labelling of hybridized fragments (PCR-SSOP) (Immucor GTI Diagnostics Inc. Waukesha USA) in combination with genomic DNA sequencing by Sanger methodology (PCRSBT).
- RNA/NanoString analysis of targeted gene expression related to activation/function of B cells, T cells, microglia, and other interleukin/ chemokine signaling. Whole blood/CSF will be collected using PAXgene® Blood RNA tubes (Qiagen) shipped to the centers. Total RNA will be extracted using PAXgene® Blood RNA Kit (Qiagen). RNA samples are quantified using Qubit 2.0 Fluorometer (Life Technologies) and RNA integrity is determined with Agilent 2100 Bioanalyzer

(Agilent Technologies). Expression levels of 44 genes related to immunological pathways and cytokines (Annex, Table) will be measured with the nCounter® Digital Analyzer (NanoString), as reported (*Armangue et al., Mol Genet Metab 2017;122:134-9*). Twenty healthy participants will serve as controls (single evaluation).

- NfL levels, determined in serum and CSF using the SiMoA Quanterix technique, as reported (*Guasp et al., Neurology 2022;98:e1489-98*). Age- and sex-matched healthy participants from previous studies will serve as controls. These studies will provide a signature of molecular biomarkers in the acute and chronic stages. We expect they will correlate with the clinical features assessed in Aim1 and will assist in treatment decisions.

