1.1. Patient recruitment and number of patients. 20 LGI1 patients will be recruited: families and patients will be approached during the acute phase of the disease and invited to participate in the study after hospital discharge.

Identification of patients will be done in (1) our hospital, (2) through a network of Spanish hospitals (already in place), and (3) the Neuroimmunology lab at HCB/IDIBAPS (referral center for autoimmune encephalitis). Informed consent and general information through a structured questionnaire will be obtained from participants/legal guardians. Regarding the number of patients, we have selected 20 patients based on our published experience with another autoimmune disease (NMDAR encephalitis) and a previous pilot study with anti-LGI1 encephalitis (used as external control group who did not have remote cognitive training). In both studies, the number of ~20 patients was informative.

Exclusion criteria include: patients unable to travel to our center, and previous history of psychiatric or neurologic diseases (eg, schizophrenia, dementia, stroke) that may interfere with the proposed studies. All patients will have a preliminary assessment of their interest in participation and any of the indicated incompatibilities

7. Treatment and calendar of the study

In-person visits include 3 visits during the post-acute stage:
V1 (after hospital discharge, ~1-3 weeks after symptom onset),
V2 (6 months),
and V3 (1 year) (Fig D).

[figure not shown]

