Each visit consists of ~1 day and 1 night at Hospital Clínic (distributed in 1/2 day, 1 night, and 1/2 day) during which they undergo clinical assessments and tests according to a pilot study: neurologic and cognitive assessment, EEG, ANS, EMG, brainstem reflex study and video-polysomnography. At V2 we will obtain an MRI (to compare with that of the acute phase). We will also obtain and the blood and serum. During the post-acute stage (by the time that patients will come to Hospital Clínic de Barcelona), blood and CSF samples will be obtained for identical studies as those performed in the acute stage serum and CSF samples. Two lumbar punctures (LP) will be performed, after informed consent, one at the first presential visit (V1) and the other at the last presential visit (V3). After the first visit, patients/families will be instructed to keep remote cognitive training for 6 months. The frequency of cognitive training is suggested by data from our pilot study in which 90% of patients had cognitive abnormalities at V1 and the improvement (albeit partially; without cognitive training) mainly occurred during the first 6 months. These patients will serve as external controls.

Summary:

V1: neurologic and cognitive assessment, EEG, ANS, EMG, brainstem reflex study and video-polysomnography. Blood and serum examination. Lumbar puncture

V2: neurologic and cognitive assessment, EEG, ANS, EMG, brainstem reflex study and video-polysomnography. MRI. Blood and serum examination

V3: neurologic and cognitive assessment, EEG, ANS, EMG, brainstem reflex study and video-polysomnography. Blood and serum examination. Lumbar puncture

Presential visits

- Presential standard neuropsychiatric examinations and cognitive assessments will be conducted as per routine clinical practice and with a reported panel of neurological functional, cognitive and psychiatric tests. Total time ~4h spread over 3 visits (the exact timetable can be adapted to patients' preferences and the length of the interviews will vary according to patients' clinical status; the times are indicative and are overestimated to be sure). These clinical evaluations will take place in the same room where the patients will sleep, and patients will have enough pauses in between to rest, eat/drink and go for a walk outside the hospital with their relatives.

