Human studies: Cross-sectional comparisons among the 2 groups of patients will be done with Analysis of Covariance (ANCOVA) and Chi-Squared tests, as appropriate. Post-hoc analyses with Bonferroni correction for post-hoc multiple comparisons will be applied to all analyses. Analysis of inter- and intragroup differences in the longitudinal follow-up will be done using multilevel linear mixed-effect (LME). Lme4 R package (version 1.1-27.1) will be used to fit LME models. Comparisons will be done with emmeans library (version 1.7.3) and Tukey method for post-hoc correction for multiple testing. The global tendency of recovery of cognitive deficits in patients receiving or not cognitive training will be assessed with the Cochran-Armitage test for trend. All analyses will be addressed considering a two-tailed type I error of 5% with statistical

significance set at p-value <0.05, using SPSS (version 25; IBM Corp, Armonk, NY) and R package (version 4.1.2; Vienna), as previously reported (*Guasp et al., Lancet Neurol 2022;21:899-910*).

Animal studies: Animal behavior with multiple determinations in time (e.g., recognition of new object) will be analyzed using repeated measures two-way analysis of variance (ANOVA). Behavioral studies with a single time determination (e.g., depressive behavior) will be analyzed with one-way ANOVA or Mann-Whitney-U for skewed distributions (e.g., tail suspension). The intensity of IgG deposits in brain and electrophysiological studies (long-term potentiation) will be analyzed with two-way ANOVA. The reactivity intensity of the antibodies of patients in HEK cells (CBA), neuron cultures, or brain tissue, or quantification of synaptic markers (e.g., GluN1, PSD95) or activated microglia, in a single time determination, will be analyzed by one-way ANOVA. Post-hoc analyses for all experiments will use Bonferroni correction for multiple testing. A p value of <0.05 will be considered significant and the α -error will be set to 0.05. Analyses will be done with GraphPad Prism v7 (*Planagumà et al., Ann Neurol 2016;80:388*).

9. Risks and benefits for participants in the study

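### Does counting deficits over 8 cognitive domains here, against 6 in the external controls, bias the comparison against training?

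*Protocol*

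**What the plan says.** Section 4.1, item 1.1, describes the cognitive assessment as a "Battery of 16 tests encompassing 8 cognitive domains" and lists the eight. Section 2 (Justification, first challenge) describes the earlier anti-LGI1 cohort: "24 patients with anti-LGI1 encephalitis were invited to come to our center", of whom "most (90%) had deficits in 1 or more of 6 cognitive domains at the first visit (V1"; then "65% had cognitive deficits at V2 (6 months), and 62% at V3 (1 year".

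That cohort is the comparator. Objective 2 in Section 4 says "Findings will be compared with a previously studied external control group of patients with anti-LGI1 encephalitis", and Section 7 says of the pilot patients that "These patients will serve as external controls". Section 6 sets the new cohort's size: "20 LGI1 patients will be recruited".

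Section 8 plans ANCOVA and chi-squared tests for cross-sectional comparisons, linear mixed-effects models for follow-up, and a Cochran-Armitage trend test for "The global tendency of recovery of cognitive deficits in patients receiving or not cognitive training". It does not define a deficit or give a domain count for that test. Hypothesis 2 in Section 3 concerns performance on memory and executive tests.

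**The concern.** The chance of at least one deficit cannot fall, and usually rises, as more domains are examined. If the six control domains sit inside the eight used here and the cut-offs match, the same patient is at least as likely to be called impaired, and no more likely to be called recovered, in the trained cohort. The Cochran-Armitage test works on proportions with a deficit, so it would carry this difference. The difference would run against training and could hide a benefit or look like harm.

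Section 5 says the controls need no new visits, which at first suggests that missing domains cannot be filled in on their side. With 20 trained patients, there is little room for an avoidable artefact.

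**Working it through.** **Is there a figure to reproduce?** No. The 90%, 65% and 62% are observed results in the earlier cohort, and the protocol gives no power or effect size for the 20 patients. The only calculation possible is of the counting effect, if it occurs.

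**Inputs from the protocol:** any-of-6 deficit at V1 90%; deficit at V2 65% and V3 62%, read as the same any-of-6 measure; 24 controls; 20 trained patients; two-sided 5% level.

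**Assumptions not in the protocol:** equal impairment rate q in every domain, one cut-off, the six domains nested in the eight, and a range of between-domain correlations.

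**Independent domains.** With P = 1 − (1 − q)^6, the any-of-8 rate is 1 − (1 − P)^(8/6).

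- V1: 1 − 0.10^(4/3) = 95.4%
- V2: 1 − 0.35^(4/3) = 75.3%
- V3: 1 − 0.38^(4/3) = 72.5%

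**Correlated domains.** In an equicorrelated latent-normal model, q is solved so that any-of-6 equals the reported rate, and any-of-8 is then computed.

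| Correlation | V1 (90%) | V2 (65%) | V3 (62%) |
|---|---|---|---|
| 0 | 95.4% | 75.3% | 72.5% |
| 0.3 | 93.3% | 71.7% | 68.9% |
| 0.5 | 92.5% | 70.1% | 67.2% |
| 0.7 | 91.7% | 68.6% | 65.7% |
| 0.9 | 90.9% | 66.9% | 64.0% |

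The rise at V2 and V3 is therefore about 2 to 10 points.

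**Change across visits.** V1 is inflated too, which offsets part of the effect if recovery is read as a fall over time. The reported V1-to-V3 fall is 90 − 62 = 28 points. On any-of-8 it becomes 95.4 − 72.5 = 22.9 (independence), 92.5 − 67.2 = 25.3 (correlation 0.5) or 90.9 − 64.0 = 26.9 (correlation 0.9). The loss is about 5, 3 or 1 points.

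**Effect on a test, near the worst case.** Suppose training truly lowers the V2 any-of-6 rate from 65% to 45%. Under independence the trained group would show 1 − 0.55^(4/3) = 54.9% on any-of-8, an apparent difference of 65 − 54.9 = 10.1 points instead of 20. With 24 against 20 patients, normal-approximation power falls from about 26% to 10%. The 20-point benefit is an illustration only.

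**Does the protocol set up this mismatch?** Three things must all be true.

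1. *Trained patients are scored as any of 8.* Section 4.1 says what the battery covers. It gives no rule for calling a patient impaired.
2. *Controls stay at any of 6.* The figure in Section 2 is background. Section 8 does not say the controls enter through published percentages. No new visits, as Section 5 states, is not the same as no existing test data.
3. *The eight add content the controls were never tested on.* Section 5 says the study follows the protocol developed for earlier studies, including the control study. Section 9 (Risks and benefits) says the earlier anti-NMDAR and anti-LGI1 studies had the same test burden at in-person visits. Both fit one battery grouped two ways. The list in Section 4.1 allows this: intelligence quotient is a global measure, and working memory and learning could be one group or two.

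The protocol states none of the three, and what it says bears against the third.

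**The case for a change.** The best argument for a change is that the protocol gives different domain counts for two groups it plans to compare while saying they share a protocol. A test on deficit proportions is explicitly planned. The study is open-label with an external control, so a deficit rule chosen after the new results are seen could be chosen more than one way. One sentence would settle it.

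Some of this stands. The 6 and the 8 are not reconciled, and if all three conditions held, the direction would be as described. But the argument shows that a definition is unstated, not that a stated rule gives a wrong answer. Scoring rules and impairment cut-offs are commonly left to a statistical analysis plan, which may exist but is not shown. The same centre ran the control study, so re-scoring both cohorts on a shared set of domains is the natural course.

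Nor is restricting the comparison to six domains clearly right. The protocol does not name the six or show that they are nested in the eight. If both cohorts took the same tests, that restriction would discard usable control data.

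**Conclusion.** No change is needed. The difference in domain count is real, but the bias is conditional on a scoring scheme the protocol does not adopt. If it were adopted, the trained group's deficit rate would be inflated by about 2 to 10 points at V2 and V3, and the V1-to-V3 fall would shrink by about 1 to 5 points. One patient in 20 is 5 points. These sizes rest on equal impairment rates, nested domains, a common cut-off and assumed correlations from 0 to 0.9. They would be smaller if the added domains were less often impaired than the six or overlapped with them.

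Only a binary any-domain comparison could be affected. ANCOVA and mixed models on test scores, and Hypothesis 2, do not depend on how many domains are counted. What remains is an unstated common deficit definition, which analysts with access to both cohorts would be expected to apply as a matter of course.
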